#### **6.2.5 End of Study**

After the follow-up period, all patients will return to the study center for the EOS visit on Day 45. If any objective reaction occurred at Day 14/15, the BPCFC will not be required but may be performed at the discretion of the Investigator on Day 45 and the symptoms will be monitored (See [Section 6.1.1](#) and [Section 6.1.2](#)). If the Investigator decides to perform the BPCFC, it can be completed in 2 days (one challenge on Day 45 and the second challenge on Day 46) if the Investigator feels that it is the best for patient's safety and convenience. Otherwise all patients will undergo the challenges (peanut challenge and placebo challenge) on Day 45 (EOS visit) itself. All blood samples scheduled for the EOS visit will be collected on Day 45 (EOS visit) regardless of splitting the BPCFC assessments. Additional procedures will be carried out in accordance with the Schedule of Events in [Table 4.1](#).

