### **7.1.1.1 Reporting of Adverse Events**

All AEs, regardless of severity occurred during the study (screening, treatment, or follow-up period) are to be recorded on the appropriate AE pages (either ‘serious’ or ‘non-serious’) in the eCRF. All AEs reported prior to IP administration will also be recorded on the medical history CRF page. The Investigator should complete all the details requested including dates of onset, severity, action taken, outcome, and relationship to the IP. Each event should be recorded separately.

The ANB020 or placebo infusion may be slowed or interrupted for patients experiencing infusion-related AEs. Following the infusion, all patients will be observed for fever, chills, rigors, hypotension, nausea, or other infusion-related AEs.

All SAEs (as described in [Section 7.1.1](#)) that occur after the patient has signed informed consent (including the protocol defined follow-up period), regardless of judged relationship to the IP, or after the study period, if considered serious and related to IP or to the patient’s participation in the study, must be reported to QuintilesIMS within 24 hours of the Investigator’s knowledge of the event. The SAE reporting will originate in the electronic data capture (EDC) system and an email will be sent to the designated responsible parties defined in the Safety Plan. The paper SAE form is in place as a back-up in the rare event that EDC is not accessible to the reporter of the SAE and the paper SAE form should be sent to [QLS\\[contact]](mailto:[contact]).

The following documents should be submitted to QuintilesIMS Safety:

- Serious Adverse Event Report Form.
- The following eCRFs or de-identified source documents:
  - Demographics page(s).
  - Medical history page(s).
  - Adverse event page(s).
  - Concomitant medication page(s).
  - Hospital discharge summary: If the patient is hospitalized because of or during the course of an SAE, then a copy of the hospital discharge.

Following are Investigator responsibilities:

- Record diagnosis instead of signs and symptoms when available using accepted medical terminology.

- The events recorded on the safety event report form must be consistent with the information entered on the respective CRFs.
- Include any relevant medical history, concurrent illnesses, and concomitant medicines.
- Include treatment(s) provided.
- The Investigator must assess causality at the time of the first SAE notification.

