18.1. ADVERSE EVENTS

Adverse Events (AEs) will be coded using MedDRA Version 19.1.

Treatment emergent adverse events (TEAEs) are defined as AEs that started or worsened in severity on or after the date and time of the IP infusion or if the event represents an exacerbation of a condition observed pre-treatment. This excludes AEs due to BPCFC. AEs due to BPCFC during screening visit will be captured in medical history events.

Non treatment emergent adverse event (Non-TEAE) will be defined as any AE that started after the informed consent form has been signed and before the first dose of study medication and did not qualify for TEAE in terms of severity.

Adverse events with missing start dates will be considered treatment-emergent. AEs with missing stop dates or with stop dates after the end of the study date will be considered to have been ongoing at the end of the study.

The relationship to investigational product will be presented as "Related" versus "Not Related". Here the relationship categories "Unrelated" and "Unlikely" collected in the eCRF will be mapped to "Not Related", while the categories "Possible", "Probable" and "Unknown" will be mapped to "Related".

For each treatment, numbers of events, patients experiencing adverse events and percentage will be tabulated. The following summary tables will be provided by system organ class and preferred term for each treatment group:

- o number of patients with at least one TEAE
- o number of patients with at least one serious TEAE

Document: \\ieedc-nas01a\biosdata\AnaptysBio\ANB020\CYA74393\Biostatistics\Documentation\SAP\Final2018-02-07
Author: [REDACTED] Version Number: Final 1.0
Version Date: 07Feb2018

STATISTICAL ANALYSIS PLAN

AnaptysBio Inc
PROTOCOL ANB020-003
Page 26 of 36

- o number of patients with at least one TEAE by severity
- o number of patients with at least one TEAE by relationship to IP
- o number of patients with at least one TEAE leading to discontinuation from the study
- o number of patients with at least one TEAE leading to interruption of IP
- o number of patients with at least one TEAE leading to death
- o number of patients with non-TEAE
- o number of patients with AEs due BPCFC

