When calculating the number of patients who experience an AE, an event that occurred one or more times on treatment will contribute one observation to the numerator and denominator for all safety patients exposed to ANB020 or placebo for the respective treatment, i.e., the event will be counted only once per SOC and per PT with highest severity and worst relationship with IP.

Listings will be provided for TEAEs, Serious TEAEs, TEAEs leading to discontinuation from study or of IP, and TEAEs leading to deaths for safety analysis set.

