Persistent or Significant Disability/ Incapacity	xx (xx x)	xx (xx x)	xx (xx x)
Congenital Abnormality/ Birth Defect	xx (xx x)	xx (xx x)	xx (xx x)
Other Medically Significant Events	xx (xx x)	xx (xx x)	xx (xx x)
Patients who Discontinued from the Study Due to TEAE			
	xx (xx x)	xx (xx x)	xx (xx x)

Source: Listing 16 3 1 1, 16 3 2 1, 16 3 3 1, 16 3 4 1

Note:

- N is the number of patients within each treatment group under Safety Analysis Set
- Adverse Event terms are coded using latest version of MedDRA
- Patients experiencing multiple events are counted only once within the treatment group
- Percentages are based on number of patients within each treatment group under Safety Analysis Set (N)
- AE- Adverse Event, TEAE- Treatment Emergent Adverse Events

Programming Note (not part of table): For count of TEAEs, use the coded term (preferred term)

Document: \\ieedc-nas01a\biosdata\AnaptysBio\ANB020\CYA74393\Biostatistics\Documentation\SAP\Draft\2018-02-07
Author: [REDACTED]

Version Number: Draft 3.0
Version Date: 07Feb2018

Table 14 3 1 2
TEAE by System Organ Class and Preferred Term – Safety Analysis Set

System Organ Class Preferred Term	ANB020 (N=XX)	Placebo (N=XX)	Total (N=XX)
Number of Patients with at least one TEAE	xx (xx x)	xx (xx x)	xx (xx x)
System Organ Class 1	xx (xx x)	xx (xx x)	xx (xx x)
Preferred Term 1	xx (xx x)	xx (xx x)	xx (xx x)
Preferred Term 2	xx (xx x)	xx (xx x)	xx (xx x)
System Organ Class 2	xx (xx x)	xx (xx x)	xx (xx x)
Preferred Term 1	xx (xx x)	xx (xx x)	xx (xx x)

Source: Listing 16 3 1 1, 16 3 2 1, 16 3 3 1, 16 3 4 1

Note:

- N is the number of patients within each treatment group under Safety Analysis Set
- Adverse Event terms are coded using System Organ Class and Preferred term using latest version of MedDRA
- Patients experiencing multiple events within the same SOC or PT are counted only once under those categories
- Percentages are based on number of patients within each treatment group under Safety Analysis Set (N)

Programming Note (not part of table):

- Table will be sorted in decreasing frequency of system organ class and preferred term of total column. Include "Uncoded" if events are not coded
A subject can have one or more preferred terms reported under a given system organ class
- Similar tables will be generated for Safety Analysis Set as follows:

Table 14 3 1 2 1 TEAEs by Preferred Term – Safety Analysis Set

Table 14 3 1 3 Serious TEAEs by System Organ Class and Preferred Term – Safety Analysis Set

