Table 14 3 1 4 TEAEs Leading to Discontinuation from the Study by System Organ Class and Preferred Term – Safety Analysis Set

Table 14 3 1 5 TEAEs Leading to Interruption of Study Drug by System Organ Class and Preferred Term – Safety Analysis Set

Table 14 3 1 6 TEAEs Leading to Death by System Organ Class and Preferred Term – Safety Analysis Set

Table 14 3 1 7 Non TEAEs by System Organ Class and Preferred Term – Safety Analysis Set

Table 14 3 1 8 Adverse Events due to BPCFC by System Organ Class and Preferred Term – Safety Analysis Set

Table 14 3 2 1
TEAEs by Severity, System Organ Class and Preferred Term – Safety Analysis Set

System Organ Class Preferred Term	ANB020 (N=XX)			Placebo (N=XX)		
	Mild	Moderate	Severe	Mild	Moderate	Severe
Number of Patients with at least one TEAE by Severity	xx (xx x)	xx (xx x)	xx (xx x)	xx (xx x)	xx (xx x)	xx (xx x)
System Organ Class 1	xx (xx x)	xx (xx x)	xx (xx x)	xx (xx x)	xx (xx x)	xx (xx x)
Preferred Term 1	xx (xx x)	xx (xx x)	xx (xx x)	xx (xx x)	xx (xx x)	xx (xx x)
Preferred Term 2	xx (xx x)	xx (xx x)	xx (xx x)	xx (xx x)	xx (xx x)	xx (xx x)
System Organ Class 2	xx (xx x)	xx (xx x)	xx (xx x)	xx (xx x)	xx (xx x)	xx (xx x)
Preferred Term 1	xx (xx x)	xx (xx x)	xx (xx x)	xx (xx x)	xx (xx x)	xx (xx x)

Source: Listing 16 3 1 1, 16 3 2 1, 16 3 3 1, 16 3 4 1

Note:

- N is the number of patients within each treatment group under Safety Analysis Set
- Adverse Event terms are coded using System Organ Class and Preferred term using latest version of MedDRA
- Patients experiencing multiple events within the same SOC or preferred term are counted only once under those categories
- Percentages are based on number of patients within each treatment group under Safety Analysis Set (N)
- Patients experiencing the same event with different severity level are counted under the most severe occurrence

Programming Note (not part of table):

- Table will be sorted in decreasing frequency of system organ class and preferred term of total column. Include "Uncoded" if events are not coded
- A subject can have one or more preferred terms reported under a given system organ class

Table 14 3 2 1
TEAEs by Severity, System Organ Class and Preferred Term – Safety Analysis Set

System Organ Class Preferred Term	Mild	Total (N=XX)	
		Moderate	Severe
Number of Patients with at least one TEAE by Severity	xx (xx x)	xx (xx x)	xx (xx x)
System Organ Class 1	xx (xx x)	xx (xx x)	xx (xx x)
Preferred Term 1	xx (xx x)	xx (xx x)	xx (xx x)

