Programming Note (not part of table): Sort by patient number, AE number, start date

Document: \\ieedc-nas01a\biosdata\AnaptysBio\ANB020\CYA74393\Biostatistics\Documentation\SAP\Final\2018-02-07

Author: [REDACTED]

Version Number: Final 1.0

Version Date: 07Feb2018

Listing 16 2 7 4
Treatment Emergent Adverse Events Leading to Death - Safety Analysis Set

Patient No / Treatment	Age/ Gender/ Race	AE Number	System Organ Class/Preferred term/Verbatim Text	Start Date/ End Date	Did AE occur prior to the start of IP infusion?	AE Severity	Action taken with the study drug	Relationship to study drug	Cause and Date of Death	Did the AE cause the subject to discontinue from the study?	Was subject treated for AE?
XXX/XXX	32/ Male/ Race	XXXX	XX/xx/xx	DDMMYYYY / DDMMYYYY	No	Severe	Dose interrupted	Unlikely	XXX/ DDMMYY YY	Yes	No
XXX/XXX	31/ Female/ Race	XXXX	XX/xx/xx	DDMMYYYY / DDMMYYYY	Yes	Mild	Drug permanently discontinued	Possible	XXX/ DDMMYY YY	Yes	Yes
XXX/XXX	28/ Female/ Race	XXXX	XX/xx/xx	DDMMYYYY / DDMMYYYY	Yes	Moderate	Dose reduced	Probable	XXX/ DDMMYY YY	No	Yes
...											

Programming Note (not part of table): Sort by patient number, AE number, start date

Document: \\ieedc-nas01a\biosdata\AnaptysBio\ANB020\CYA74393\Biostatistics\Documentation\SAP\Final\2018-02-07

Author: [REDACTED]

Version Number: Final 1.0

Version Date: 07Feb2018

Listing 16 2 7 5
Adverse Events Due to BPCFC - Safety Analysis Set

Patient No / Treatment	Age/ Gender/ Race	AE Number	System Organ Class/Preferred term/Verbatim Text	Start Date/ End Date	Did AE occur prior to the start of IP infusion?	AE Severity	Final Outcome	Action taken with the study drug	Relationship to study drug	Seriousness Criteria ^[1]	Did the AE cause the subject to discontinue from the study?	Was subject treated for AE?
XXX/XXX	32/ Male/ Race	XXXX	XX/xx/xx	DDMMYYYY /	No	Severe	Recovered	Dose interrupted	Unlikely	XXX	Yes	No
XXX/XXX	31/ Female/ Race	XXXX	XX/xx/xx	DDMMYYYY /	Yes	Mild	Fatal	Drug permanently discontinued	Possible	XXX	Yes	Yes
XXX/XXX	28/ Female/ Race	XXXX	XX/xx/xx	DDMMYYYY /	Yes	Moderate	Lost to follow-up	Dose reduced	Probable	XXX	No	Yes
...												

Document: \\ieedc-nas01a\biosdata\AnaptysBio\ANB020\CYA74393\Biostatistics\Documentation\SAP\Final\2018-02-07

Author: [REDACTED]

Version Number: Final 1.0

Version Date: 07Feb2018

Listing 16 2 8 1
Clinically Significant Laboratory Results - Safety Analysis Set

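### Food-challenge adverse events are pooled over the Day 14 and Day 45 challenges and divided by all safety patients, although who is challenged at Day 45 depends on the Day 14 result

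*SAP*

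**What the plan says.** SAP 18.1 excludes adverse events due to the blind placebo-controlled food challenge (BPCFC) from TEAEs and lists a separate output, the "number of patients with AEs due BPCFC". The counting rule there is that "an event that occurred one or more times on treatment will contribute one observation to the numerator and denominator for all safety patients exposed" to the arm's treatment, once per SOC and preferred term.

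Two shells implement it. Table 14.3.1.1 has BPCFC rows for the number of events and the number of patients, with the note "Patients experiencing multiple events are counted only once within the treatment group". Table 14.3.1.8, "Adverse Events due to BPCFC by System Organ Class and Preferred Term – Safety Analysis Set", reuses the TEAE shell. Neither has a visit column, and both use the Safety Analysis Set as denominator, which is everyone who received any portion of an infusion (SAP 5.4).

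Protocol 6.1.1 schedules challenges at screening, Day 14 and Day 45. Protocol 6.2.5, as changed by Amendment 5 of 01 DEC 2017, says: "If any objective reaction occurred at Day 14/15, the BPCFC will not be required but may be performed at the discretion of the Investigator". The SAP is dated 07 Feb 2018 but names Amendment 3 as its source (SAP 1) and reports no changes from the protocol analysis (SAP 3.3).

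**The concern.** An AE due to a challenge can occur only when a challenge is given. After dosing, the number of challenges a patient receives now depends on that patient's Day 14/15 result, and the denominator does not reflect this. It also keeps patients who were dosed but never challenged afterwards, such as those who leave before Day 14 and are replaced under Protocol 4.3.5.

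Safety is a primary objective, and a challenge reaction is a hazard built into this design. Because these reactions are taken out of TEAEs, the TEAE tables by seriousness, severity and relatedness omit them. The two outputs named above are then the only by-arm AE counts of challenge reactions. A reader will take their percentages as a comparison of the arms, without knowing whether a reaction came at two or six weeks, or out of how many challenges.

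**Working it through.** **Inputs from the documents.** Protocol 6.2.2 gives 15 ANB020 and 5 placebo patients. This reproduces: 20 × 3/4 = 15 and 20 × 1/4 = 5. The documents state no reaction rate for any visit.

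**Assumed inputs.** Let p be the probability of a challenge AE at Day 14 and q the probability at Day 45 among Day 14 non-reactors, with subscripts P (placebo) and A (ANB020). High values of p on placebo are plausible because eligibility requires a reaction to peanut at screening (Protocol 4.3.1). For simplicity a challenge AE is equated with an objective reaction. In practice an AE may be subjective and would not trigger the Day 45 waiver.

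**1. Any-event patient row.** Pooled incidence = p + (1 − p)q. The change in the placebo-minus-ANB020 difference is

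Day 14 difference − pooled difference = (1 − pA)qA − (1 − pP)qP,

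so the difference shrinks only if qA/qP > (1 − pP)/(1 − pA).

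| Placebo p/q | ANB020 p/q | Day 14 difference | Pooled incidence | Pooled difference |
|---|---|---|---|---|
| 0.95/0.95 | 0.5/0.5 | 45 points | 99.75% v 75% | 24.75 points |
| 0.8/0.8 | 0.4/0.1 | 40 points | 96% v 46% | 50 points |
| 0.6/0.6 | 0.3/0.3 | 30 points | 84% v 51% | 33 points |

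The threshold for qA/qP is 0.05/0.5 = 0.10 in the first case, where the actual ratio is 0.53. It is 0.2/0.6 = 0.33 in the second, where the ratio is 0.125. With no drug effect both differences are zero.

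The formula is the same whether or not Day 14 reactors are challenged again, since they are already in the numerator. What moves this row is the second challenge of the non-reactors.

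**2. Event-count row.** Assume 0.95 v 0.5 at each challenge and one event per reaction.

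- Everyone re-challenged: 2 × 0.95 = 1.90 v 2 × 0.5 = 1.00 events per patient, difference 0.90.
- Reactors skip Day 45: 0.9975 v 0.75, difference 0.25.

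Here the waiver does the work. Challenges per patient are 1 + (1 − p), which is 1.05 on placebo and 1.50 on ANB020.

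**3. SOC and preferred-term rows.** Same rates, with a given term assumed to occur independently in 40% of reactions.

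- Day 14 only: 0.4 × 0.95 = 38% v 0.4 × 0.5 = 20%, difference 18 points.
- Pooled, everyone re-challenged: 1 − 0.62² = 61.6% v 1 − 0.80² = 36.0%, difference 26 points.
- Pooled, reactors skip: 0.4 × 0.9975 = 39.9% v 0.4 × 0.75 = 30.0%, difference 10 points.

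A reactor who skips Day 45 can show a second term only if challenged again, so the waiver changes these rows too.

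**The case against.** The strongest objection is that the consequence is limited. SAP 18 plans no statistical comparison of safety data. The Day 14 effect is carried by the tolerated dose and the OFC symptom score, both tabulated separately for Day 14 and Day 45 (Tables 14.2.1.1 and 14.2.2.1). With 20 patients, the dates in Listing 16.2.7.5 allow a by-visit count by hand. All of this stands and keeps the point modest. Dose and score tables are not AE counts, however, and a listing does not correct a misleading percentage.

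Three stronger readings are tempting and are not supported.

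- *The waiver for Day 14 reactors biases the patient count.* For the any-event row it does not, as step 1 shows.
- *The pooled difference always understates protection.* It need not. The Day 45 rate applies only to Day 14 non-reactors, who may be less reactive, and Protocol 4.2 reports complete ex vivo inhibition up to 43 days at this dose, so a low qA is possible. The second and third cases in the table widen.
- *Screening reactions would push both arms towards 100%.* Protocol 7.1.1.1 does say "All AEs reported prior to IP administration will also be recorded on the medical history CRF page", in addition to the AE pages, and Listing 16.2.7.5 has a column headed "Did AE occur prior to the start of IP infusion". But SAP 12 and 18.1 assign screening BPCFC events to medical history, and the same column stands in the TEAE, discontinuation, serious and death listings, so it looks like a template item. One clarifying sentence is enough.

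**Conclusion.** The point holds as a defect of descriptive reporting that should be corrected. The only by-arm AE counts of challenge reactions pool two post-dose challenges over a denominator that ignores who was challenged, and the SAP was not brought up to Amendment 5.

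The any-event row is a cumulative incidence over two challenges and would be so even if everyone were re-challenged. Its between-arm difference may be smaller or larger than at Day 14 (45 to 25 points, or 40 to 50 points, in the cases shown), and the table does not let a reader tell which. The waiver itself affects the event count (0.90 v 0.25 per patient) and the SOC and preferred-term rows (26 v 10 points). These sizes rest entirely on assumed reaction rates, on one event per reaction, and on a term occurring in 40% of reactions. The direction and size in this trial cannot be known from the documents.

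**What to change.** In SAP 18.1, the BPCFC rows of Table 14.3.1.1, and Table 14.3.1.8:

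- Report AEs due to BPCFC separately for the Day 14/15 and Day 45/46 challenges.
- Use as denominator the patients who started any part of the BPCFC, placebo or peanut, at that visit. Placebo is given first and a challenge stops on signs of a reaction (Protocol 6.1.1), so a denominator of peanut challenges alone could miss a patient who is in the numerator.
- Use Day 14/15 to describe the arms side by side. Label Day 45/46 as a selected subset and show it by Day 14 reaction status.
- State that screening BPCFC events are excluded because they are reported as medical history.
- Update the SAP's source protocol to Amendment 5.

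The cost is SAP text and two table shells. AE dates and challenge dates are already planned for listing (Listings 16.2.7.5 and 16.2.6.1), so events can be assigned to a challenge without new data. The small downside is that Day 45 percentages rest on few patients: at the 0.95 and 0.5 rates with all reactors skipping, about 5 × 0.05 = 0.25 placebo and 15 × 0.5 = 7.5 ANB020 patients.

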18.2. DEATHS

The number of patients with at least one TEAE leading to death will be summarized and listed as described above.

18.3. LABORATORY EVALUATIONS

Results from both the central and local laboratory will be included in the reporting. Central laboratory results will be reported for hematology, clinical chemistry and urinalysis. Local urine pregnancy test results will be reported as well. The actual and change from baseline values for each laboratory parameter will be summarized using descriptive statistics (n, mean, SD, median, and range) by treatment and all available visits.

The following summaries will be provided for laboratory data:

- o Incidence of abnormal values according to normal range criteria
- o Potential clinical significance of clinical laboratory assessments

A shift table will be presented of the potential shifts from baseline to the final measurement of values that are clinically relevantly high or low.

A listing of patients with abnormal values or clinically significant changes will be presented.

Document: \\ieedc-nas01a\biosdata\AnaptysBio\ANB020\CYA74393\Biostatistics\Documentation\SAP\Final2018-02-07
Author: [REDACTED] Version Number: Final 1.0
Version Date: 07Feb2018

Template No: CS_TP_BS016 Revision 4
Effective Date: 01Apr2016

Reference: CS_WI_BS005

STATISTICAL ANALYSIS PLAN

AnaptysBio Inc
PROTOCOL ANB020-003
Page 27 of 36

Hematology and clinical laboratory data will be reported in System International (SI) units.

